7.2. Discontinuation of Study Intervention

Not applicable for Part A.

In Part B, a participant will be permanently withdrawn from study treatment if any of the following symptoms or abnormalities occur, and an investigation will be carried out as described below. After withdrawal of treatment (under these conditions), where possible participants should complete the Early Withdrawal visit and be followed up for safety monitoring.

Study medications will be discontinued, and the participant withdrawn from the study in the event of any of the following:

- A serious infection (including COVID-19)
- Pregnancy
- Severe or serious hypersensitivity reactions, including anaphylaxis
- If the liver chemistry stopping criteria (Section 7.2.1) or QTc stopping criteria (Section 7.2.2) are met.
- Other serious or severe adverse events, at the discretion of the Investigator, after consultation with the GSK Medical Monitor.

Clinically significant deterioration of index knee pain or requiring recurrent rescue medication beyond the level permitted, at the discretion of the investigator, after consultation with the GSK Medical Monitor.

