4.1.1. Treatment Groups and Duration

The total duration of the study (from signing of the informed consent until final follow-up) for each participant will vary between cohorts (see Table 1). The screening period will be of a maximum of 28 days for all cohorts in Part A and a maximum of 42 days in Part B. Final follow-up visits will be scheduled to occur when approximately 5 half-lives of GSK3858279 have elapsed after dosing. Follow-up visits are scheduled earlier for the lowest dose group where PK parameters are expected to be below the lower limit of quantification (LLQ), and are extended by an additional 4 weeks for the top dose cohort where extended pharmacology may be observed (see Table 1 and Schedule of Activities [SoA, Section 1.3]).

In Part A, each participant will receive a single dose of study intervention (GSK3858279 or placebo), either IV or SC. The planned dosing schedule is described in Table 1, although dose levels are subject to change depending on emerging study data. The maximum dose (level) that may be administered in the study will be 10 mg/kg, both for IV and SC cohorts. See Section 4.4 for further details.

In Part B, each participant will receive SC injections weekly for 8 weeks.

Table 1 Dosing schedule and study duration

Part	Cohort	Dose of GSK3858279	Follow up (days post dosing)	Maximum study duration including screening (days)
Part A	Cohort 1 IV	Up to 0.1 mg/kg	84	112
	Cohort 2 IV	Up to 0.3 mg/kg	112	140
	Cohort 3 IV	Up to 1 mg/kg	112	140
	Cohort 4 IV	Up to 3 mg/kg	112	140
	Cohort 5 IV	Up to 10 mg/kg	140	168
Cohort 6 SC	Between 1 and 3	140	168	
	Colloit 6 SC	mg/kg (max 240 mg)		
Part B	Cohort 7 SC	240 mg	56 (Treatment)	182/183
			84(Follow Up)	

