7.3. Participant Discontinuation/Withdrawal from the Study

- A participant may withdraw from the study at any time at his/her own request or may be withdrawn at any time at the discretion of the investigator for safety, behavioural, compliance or administrative reasons.
- If the participant withdraws consent for disclosure of future information, the sponsor may retain and continue to use any data collected before such a withdrawal of consent.
- If a participant withdraws from the study, he/she may request destruction of any samples taken and not tested, and the investigator must document this in the site study records.
- At the time of study discontinuation, the participant should undergo the assessments for early withdrawal shown in the SOA.

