8.5. Immunogenicity Assessments

Serum samples will be collected from all treated participants at pre-dose and various time points post-dosing. The washout samples will be collected at the follow-up visit to minimise interference of circulating drug in the antibody assessments, see SoA (Section 1.3.5). Testing will be performed using the typical tiered approach involving screening, confirmation and titration assays [EMEA, 2017; FDA, 2014], performed by IVIVT, GSK. If sera contain potential anti-GSK3858279 antibodies, they will be confirmed by immune-competition using excess drug, followed by a titration assay.

For each participant, immunogenicity results, including the incidence and titres, will be reported.

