7.1.4. Strategy for Intercurrent (Post-Randomization) Events

There is one intercurrent event that is of interest:

1. Treatment Withdrawal (Participant discontinues the study treatment but continues to stay in the study)

No imputations would be carried out if there are missing data due to intercurrent events.

A hypothetical strategy will be used to estimate what the treatment effect would have been had the subject not experienced the intercurrent event. Data collected after the occurrence of the Intercurrent Event will be listed but not used in summary stats and stats analysis TFLs. Since the dosing interval in this study is 7 days, the date of occurrence of the treatment withdrawal intercurrent event will be defined as the date of the first missed dose of study treatment i.e. date of last dose of study treatment + 7 days. Pain scores are measured daily in the evening, therefore pain scores on or after the date of last dose of study treatment + 7 days will be considered as occurring after treatment withdrawal.

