14.6.2. Study Population

Age

 • Birth date will be presented in listings as 'YYYY'. • GSK standard IDSL algorithms will be used for calculating age where birth date will be imputed as follows: 
 ◦ Any participant with a missing day will have this imputed as day '15'. ◦ Any participant with a missing date and month will have this imputed as '30th June'. • Calculated based on the screening date
Body Mass Index (BMI)

 • Calculated as Weight (kg) / [Height (m)²]
Race Category

 • The five high level FDA race categories and designated Asian subcategories will be summarised along with all combinations of high level categories which exist in the data. • The high level FDA race categories and designated Asian subcategories are: 
 ◦ AMERICAN INDIAN OR ALASKA NATIVE ◦ ASIAN 
 ◦ CENTRAL/SOUTH ASIAN HERITAGE ◦ JAPANESE HERITAGE/EAST ASIAN HERITAGE/SOUTH EAST ASIAN HERITAGE ◦ MIXED ASIAN RACE (only required if data exists) ◦ BLACK OR AFRICAN AMERICAN ◦ NATIVE HAWAIIAN OR OTHER PACIFIC ISLANDER ◦ WHITE • A subject who selects a combination of races will be counted in a row within "MULTIPLE" or within the "MIXED ASIAN RACE", not in each of the constituent terms.
Extent of Exposure

 • Number of days of exposure to study drug in Part B will be calculated based on the formula: 
 ◦ Duration of Exposure in Days = Treatment Stop Date – (Treatment Start Date) + 1+18*5 ◦ Note: The half life of the drug is approximately 18 days. Hence 5*18 =~ 90 days is added in the equation of duration of exposure. • Participants who were randomized but did not report a treatment start date will be categorised as having zero days of exposure. • The summary statistics based on the frequency of injections would be provided in the exposure display for Part B.

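### Protocol Section 7.2 gives two dispositions for the same Part B stopping events, so scheduled safety observation and the washout ADA sample can be lost

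*Protocol*

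**What the plan says.** Section 7.2 opens by permanently withdrawing the Part B participant from study treatment and says that "where possible participants should complete the Early Withdrawal visit and be followed up for safety monitoring". The sentence that introduces the list of events is different: "Study medications will be discontinued, and the participant withdrawn from the study in the event of any of the following". The list includes serious infection (COVID-19 among them), severe or serious hypersensitivity, and the liver and QTc criteria. Other serious or severe AEs are discretionary.

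Other places bear on the same events:
- Section 7.2.2 (QTc) and Appendix 6a (liver) stop study intervention only, and Appendix 6a continues monitoring.
- The COVID-19 contingency plan in Section 2.3.1 points the other way. Symptomatic or PCR-positive participants take no further part and get medical follow-up under local procedure.
- Section 7.3: "At the time of study discontinuation, the participant should undergo the assessments for early withdrawal shown in the SOA".
- Section 8.6.1 collects AEs until the follow-up visit and puts no duty on investigators to look actively for events in people who have left.
- Section 4.1.1: "Final follow-up visits will be scheduled to occur when approximately 5 half-lives of GSK3858279 have elapsed after dosing".
- SAP 14.6.2: "The half life of the drug is approximately 18 days".
- Section 8.5: "The washout samples will be collected at the follow-up visit to minimise interference of circulating drug in the antibody assessments".

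**The concern.** Two sites could handle the same event in opposite ways, each with a sentence of Section 7.2 to support it. The difference matters because leaving the study changes what must be collected. Under study withdrawal, the visible text defines one set of assessments, at the time of leaving. Section 7.2 asks for safety follow-up but gives it no length, visits or samples. By contrast, Section 8.7 sets a minimum monitoring period after an overdose, expressed in half-lives and days.

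The participants affected are those who show the risks named in Section 2.3.1, such as hypersensitivity and infection. Safety is a primary objective, and Part B is the first repeat dosing in a first-in-human study, with about 25 people planned on active drug (50 randomised 1:1). A few truncated records would therefore count. If the last ADA sample is taken while drug is circulating, it is not the washout sample that Section 8.5 describes. That could affect SAP Table 2.37, which splits treatment-emergent AEs by highest post-baseline ADA result.

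**Working it through.** **The dispositions side by side**

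| Place | Trigger | Disposition |
|---|---|---|
| Protocol 7.2, opening | all listed | off study treatment; Early Withdrawal visit and safety follow-up where possible |
| Protocol 7.2, list sentence | all listed | off treatment and out of the study |
| Protocol 7.2.2 | QTc | off study intervention |
| Appendix 6a | liver | off study intervention, with continued monitoring |
| Protocol 2.3.1 | COVID-19 | no further participation |

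The list sentence therefore conflicts with the sentence before it for every trigger, and with a dedicated section for QTc and liver events.

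**Inputs**
- Half-life about 18 days (SAP 14.6.2).
- Final follow-up at about 5 half-lives (Protocol 4.1.1).
- Last dose Day 50, final visit Day 141 (Part B schedule of activities).
- Weekly dosing (Protocol 4.1.1), so an event during treatment normally falls within 7 days of the latest dose.

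**The plan's own figure**
- 5 x 18 = 90 days, matching the SAP exposure formula.
- A completer has 141 - 50 = 91 days after the last dose. 91 / 18 = 5.06 half-lives, and 2^(-91/18) = 3.0% of the drug remains.

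The schedule and the 5-half-life principle agree for completers.

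**An early stopper seen promptly**

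Fraction remaining t days after the last dose = 2^(-t/half-life), assuming mono-exponential decline and ignoring absorption and distribution.
- t = 2: 2^(-2/18) = 93%
- t = 7: 2^(-7/18) = 76%
- t = 14: 2^(-14/18) = 58%
- t = 18: 50%

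The documents give only the rounded 18 days, so the day-7 figure is repeated for assumed half-lives:
- 10 days: 62%
- 14 days: 71%
- 18 days: 76%
- 25 days: 82%

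More than half remains at day 7 for any half-life above 7 days.

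**Observation at stake**

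If observation ended at a visit 7 days after the last dose, 91 - 7 = 84 of the 91 days that a completer receives would be lost. This is a worst case, because it sets the safety follow-up requested in Section 7.2 to zero.

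**The case against.** The strongest reply is that follow-up is already required, and much of that stands:
- Section 7.2 itself asks for safety follow-up.
- Section 6.3.2 shows that withdrawal need not end it: an unblinded participant is withdrawn yet followed for safety if dosed.
- Section 8.6 keeps the investigator responsible for AEs that are serious, related, or the cause of discontinuation. That covers a severe but non-serious hypersensitivity reaction.
- Section 8.6.3 follows SAEs until they resolve or stabilise, and Appendix 6a does the same for liver chemistry.
- Section 8.6.1 still requires prompt notification of a related SAE that the site learns of after discharge.

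A reader might infer that these participants leave with no follow-up, or that the event that stopped treatment would go unresolved. The documents do not support either reading.

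A reader might also infer that the ADA sample at withdrawal is the only one, or that Table 2.37 will misclassify these participants. Neither can be shown. Section 8.5 samples at several post-dose times, the table uses the highest post-baseline result, and the assay's drug tolerance is not given. The Part B ADA rows are redacted, so sampling at Early Withdrawal cannot be checked.

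Nor is SAP 7.1.4 a third disposition. It defines an efficacy intercurrent event for anyone who stops dosing and remains in the study. It does not say that people meeting a Section 7.2 trigger remain.

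The reply leaves two things unanswered. None of these rules secures scheduled visits for new-onset AEs, scheduled safety laboratory tests or a washout ADA sample after early stopping. And none resolves the two sentences of Section 7.2.

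**Conclusion.** The contradiction is in the current text and has a consequence. Under one of its two readings, a participant stopped for a listed event can miss scheduled observation for new AEs, scheduled laboratory tests and the washout ADA sample, up to the plan's own horizon of about 90 days. For an event within 7 days of a dose, about 76% or more of the drug would still be present at an immediate Early Withdrawal visit.

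The size rests on three assumptions: the SAP's rounded 18-day half-life, mono-exponential decline, and an event during the dosing period. Early Withdrawal can also fall in the follow-up period, where less is lost; with an 18-day half-life, more than half the drug remains only until 18 days after the last dose. The 84 of 91 days is an upper case for a day-7 visit, not an expected loss. The effect on Table 2.37 is possible but cannot be sized.

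**What to change.** Reconcile the two sentences of Section 7.2 with each other and with Sections 2.3.1 (COVID-19 plan), 4.1.1, 7.2.2, 7.3, 8.5 and Appendix 6a, so that one disposition applies to each trigger. Then state which scheduled safety and ADA assessments apply after early stopping, and for how long, consistently with the follow-up principle in Section 4.1.1. Which events stop dosing, and which disposition is right, is for the sponsor to decide.

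The cost is mainly protocol wording, for the few participants who stop early. It may not be quite free, because the schedule is fixed from Day 1. For example, after a last dose on Day 29, 90 days falls on Day 119 (29 + 90), and the nearest contact, Day 120, is by telephone. The sponsor should say how the existing visits serve such cases.

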7.2.1. Liver Chemistry Stopping Criteria

Liver chemistry stopping and increased monitoring criteria have been designed to assure participant safety and evaluate liver event etiology.

The Liver Safety Required Actions and Follow up Assessments Section and, Liver Stopping Event algorithm can be found in Appendix 6a and Appendix 6b, respectively respectively.

7.2.2. QTc Stopping Criteria

The QTc should be based on a single (initial reading in Part A) or the average of triplicate (Part B) ECG readings obtained over a brief (e.g., 5-10 minute) recording period. See the SoA (Section 1.3) for data to be collected at the time of intervention discontinuation and follow-up and for any further evaluations that need to be completed.

A participant who meets the below QTc stopping criteria (based on the average of triplicate ECG readings) will be withdrawn from study intervention:

QTc >500 msec OR Uncorrected QT >600 msec

• For trial eligibility and discontinuation, ideally the same QT correction formula will be used for *all* participants within a single trial. However, GSK does recognize that because multiple sites from different countries may participate in a single trial, this may not always be possible since QT correction formulae pre-programmed by different manufacturers within ECG machines tend to vary. In these situations, the same QT correction formula must be used throughout the trial for an individual participant

7.2.3. Dose Adjustment Pharmacokinetic Criteria

The following criteria will apply.

7.2.4. Temporary Discontinuation

Not applicable for Part A.

For Part B, if a participant experiences a clinically significant AE that the investigator believes may be possibly, probably or definitely related to investigational product (IP) and could potentially be exacerbated by the next dose, the investigator may delay IP dosing by withholding one dose and should contact the Medical Monitor.

7.3. Participant Discontinuation/Withdrawal from the Study

- A participant may withdraw from the study at any time at his/her own request or may be withdrawn at any time at the discretion of the investigator for safety, behavioural, compliance or administrative reasons.
- If the participant withdraws consent for disclosure of future information, the sponsor may retain and continue to use any data collected before such a withdrawal of consent.
- If a participant withdraws from the study, he/she may request destruction of any samples taken and not tested, and the investigator must document this in the site study records.
- At the time of study discontinuation, the participant should undergo the assessments for early withdrawal shown in the SOA.

7.4. Lost to Follow Up

A participant will be considered lost to follow-up if he or she repeatedly fails to return for scheduled visits and is unable to be contacted by the study site.

The following actions must be taken if a participant fails to return to the clinic for a required study visit:

- The site must attempt to contact the participant and reschedule the missed visit as soon as possible and counsel the participant on the importance of maintaining the assigned visit schedule and ascertain whether or not the participant wishes to and/or should continue in the study.
- Before a participant is deemed lost to follow up, the investigator or designee must make every effort to regain contact with the participant (where possible, 3 telephone calls and, if necessary, a certified letter to the participant's last known mailing address or local equivalent methods). These contact attempts should be documented in the participant's medical record.
- Should the participant continue to be unreachable, he/she will be considered to have withdrawn from the study with a primary reason of lost to follow-up.

8. STUDY ASSESSMENTS AND PROCEDURES

After providing informed consent, participants will undergo screening assessments. After a successful Screening Period of up to 28 days (for Part A) during which screening assessments will be performed (screening assessments may be carried out over multiple days), participants will be admitted to the clinical unit on the day prior to dosing. On Day 1 they will receive a single IV or single SC dose of GSK3858279 or placebo then remain in house under supervision until discharged on Day 3. Participants will then return for outpatient visits and a follow up visit. The number of visits and the duration of the follow up period will depend on the dose level that the participant received. Details of the visits and follow up duration can be seen in the Treatment Groups and Duration section. There is a degree of flexibility around certain visits to facilitate scheduling. A visits schematic is included in Figure 1.

For Part B the maximum Screening Period will be up to 42 days (screening assessments may be carried out on multiple days) refer to Section 4.1.1 and Figure 5 for SC treatment frequency and out-patient visits.

- Study procedures and their timing are summarized in the SoA (Section 1.3).
- Protocol waivers or exemptions are not allowed
- Immediate safety concerns should be discussed with the sponsor immediately upon occurrence or awareness to determine if the participant should continue or discontinue study intervention.
- Adherence to the study design requirements, including those specified in the SoA (Section 1.3), is essential and required for study conduct.
- All screening evaluations must be completed and reviewed to confirm that potential participants meet all eligibility criteria. The investigator will maintain a screening log to record details of all participants screened and to confirm eligibility or record reasons for screening failure, as applicable.

- Procedures conducted as part of the participant's routine clinical management (eg, blood count) and obtained before signing of ICF may be utilized for screening or baseline purposes provided the procedure met the protocol-specified criteria and was performed within the time frame defined in the SoA (Section 1.3).
- The maximum amount of blood collected from each participant over the duration of the study, including any extra assessments that may be required, will not exceed 500 mL.
- Repeat or unscheduled samples may be taken for safety reasons or for technical issues with the samples.

8.1. Safety Assessments

Planned time points for all safety assessments are provided in the SoA (Section 1.3).

8.1.1. Physical Examinations

- A full physical examination will include, at a minimum, assessments of the Skin, Cardiovascular, Respiratory, Gastrointestinal and Neurological systems. Height and weight will also be measured and recorded.
- A brief physical examination will include, at a minimum, assessments of the skin, lungs, cardiovascular system, and abdomen (liver and spleen).
- Investigators should pay special attention to clinical signs related to previous serious illnesses.

8.1.2. Vital Signs

- Temperature, pulse rate, and blood pressure will be assessed following the sites local procedure.
- Blood pressure and pulse measurements will be assessed in a semi-supine position with a completely automated device. Manual techniques will be used only if an automated device is not available.
- Blood pressure and pulse measurements should be preceded by at least 5 minutes of rest for the participant in a quiet setting without distractions (eg, television, cell phones).
- Vital signs (to be taken before blood collection for laboratory tests) will consist of 1 pulse and 3 blood pressure measurements (3 consecutive blood pressure readings will be recorded at intervals of at least 1 minute). The average of the 3 blood pressure readings will be recorded on the CRF.

8.1.3. Electrocardiograms

• Continuous cardiac telemetry will be performed as per the SoA (Section 1.3). Full disclosures will be reviewed in detail and the review maintained as part of the participant's source documents.

- Triplicate or single 12-lead ECG will be obtained as outlined in the SoA (Section 1.3) using an ECG machine that automatically calculates the heart rate and measures PR, QRS, QT, and QTc intervals. Refer to Section 7.2.2 for QTc withdrawal criteria and additional QTc readings that may be necessary.
- At each time point at which triplicate ECG are required, 3 individual ECG tracings should be obtained as closely as possible in succession, but no more than 2 minutes apart. The full set of triplicates should be completed in less than 10 minutes.
- ECGs may be generated from telemetry.

8.1.4. Clinical Safety Laboratory Assessments

- Refer to Appendix 2 for the list of clinical laboratory tests to be performed and to the SoA (Section 1.3). for the timing and frequency.
- The investigator must review the laboratory report, document this review, and record any clinically relevant changes occurring during the study in the AE section of the CRF. The laboratory reports must be filed with the source documents. Clinically significant abnormal laboratory findings are those which are not associated with the underlying disease, unless judged by the investigator to be more severe than expected for the participant's condition.
- All laboratory tests, with values considered clinically significantly abnormal during participation in the study after the last dose of study intervention, should be repeated until the values return to normal or baseline or are no longer considered significantly abnormal by the investigator or medical monitor.
- If such values do not return to normal/baseline within a period of time judged reasonable by the investigator, the aetiology should be identified, and the sponsor notified.
- All protocol-required laboratory assessments, as defined in Appendix 2 must be conducted in accordance with the laboratory manual and the SoA (Section 1.3).

